Forty women ages 18–45 years will complete a protocol involving open-label treatment with standard-dose depot leuprolide to induce hypo-E2 in all women and generate HF in approximately 2/3, thereby mimicking menopause (see **Schema**). As part of the protocol, subjects will be admitted to the BWH Clinical And Translational Science Center/Center for Clinical Investigation (CCI) inpatient unit for a total of 10 nights over a 2-month period (see **Schema**). Assessments will be divided into 2 sleep blocks. Each SB includes 2 nights during which sleep is undisturbed and 3 nights during which sleep is experimentally fragmented. Using PSG, sleep patterns will be experimentally interrupted to the same target level for all subjects during all fragmented nights using auditory procedures to mimic the menopausal hot flash-associated sleep maintenance problem. The in-lab sleep blocks will be conducted: 1) during the mid-to- late follicular phase of the menstrual

cycle when E2 is high; and 2) after at least 4 weeks on leuprolide when HF are prominent in a subset of subjects.

Participants will be given a standardized eucaloric diet for several days preceding the inpatient admission, as well as for the first four days of the inpatient visit. On one day before admission, and on the final day of inpatient admissions, subjects will have an ad lib diet. Fasting adipokine levels will be measured and leptin levels will be obtained to determine the 24-hour leptin profile under standardized eucaloric diet conditions. Food intake and macronutrient composition will be assessed as key behavioral biomarkers for body fat gain when the diet is ad lib. Hunger will be measured under both eucaloric and ad lib dietary conditions. Secondary and exploratory measures of objective HF using skin conductance monitors, negative mood/affect, reward seeking behaviors, and appetite/food preference will also be obtained. Behavioral measures will continue to be assessed at home after the 2nd SB is complete.

Protocol Schema

Study Sample and Criteria

Informed consent will be obtained from up to 130 healthy non-pregnant premenopausal women 18-45 years who do not have hot flashes in order to have 40 women complete study procedures.

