- Subjects will come to one of the outpatient research units to be given an injection of leuprolide (GnRH agonist). The timing of ovulation will have been previously determined based on the collection of at least 3 menstrual cycle start dates. Leuprolide will be administered in the week prior to an expected menstrual cycle start date. If the subject starts her menstrual cycle early prior to receiving leuprolide, the protocol will be extended to the next cycle. On the day of the scheduled appointment for the injection, a urine pregnancy test will be performed to confirm that the subject is not pregnant and blood will be drawn to measure reproductive hormone levels.

Sleep Block 2 (10 days – 4 weeks after GnRH Agonist Injection)

- Subjects will be admitted for two five night stays within the BWH Clinical And Translational

Science Center/Center for Clinical Investigation (CCI) inpatient unit. Subjects will also complete at-home procedures, including an at-home PSG procedure. Subjects may log meals before inpatient admission and for up to 7 days after discharge with the app MealLogger™.

Follow-up Phase (4-12 weeks or until symptoms resolve)

- Follow-up phone call from the study coordinator 4 weeks after the final study visit and every 4 weeks thereafter to confirm resumption of menses and cessation of hot flashes (if they occurred).
- Study staff will also collect food and appetite measures that were recorded by subjects the end of Sleep Block 2
- Subjects who do not have resumption of menses or who continue to have hot flashes 4 months after receiving the leuprolide injection (3 months after final visit) will be referred to their routine medical provider for evaluation.
- A study summary letter will be sent to subjects once the final follow-up phone call has occurred. If there are any abnormal laboratory results listed in the letter that have not yet been discussed with the subject, a study clinician will call the subject to discuss prior to sending the letter.

Detailed Description of Sleep Blocks

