Assessments will be divided into 2 sleep blocks, each of which lasts 9 nights/10 days and includes 5 nights of inpatient laboratory assessment. Each block includes 2 in-lab nights during which sleep is undisturbed and 3 nights during which sleep is experimentally fragmented. Subjects will also receive an actigraphy watch and record their sleep habits before entering the lab, and for up to 7 nights after. During one night of each sleep block, subjects will use an at-home PSG to record their sleep. Subjects will return to BWH the following morning to deposit the PSG device with study staff, and to eat an ad lib breakfast.

- **At-home procedures during the Sleep Block:** Subjects will complete four days of at-home procedures before their admission to the CCI inpatient unit. On the 1st, 2nd, and 4th days, subjects will eat eucaloric meals provided by the BWH Nutrition Core. On the 3rd day, subjects will be given food provided by the Nutrition Core for that entire day, and will be allowed to consume as much as desired at home while logging their meals, snacks and drinks. On the 2nd night of the sleep block, subjects will come to Brigham and Women's to have an at-home ambulatory PSG machine attached; this machine will be removed the following morning when subjects arrive for breakfast. Eucaloric diets will approximate the current American women's diet, with approximately 15% protein, 50% carbohydrates, and 30% fat. Subjects will select each eucaloric meal from options prepared by the Nutrition Core; this selection will be done in advance of sleep blocks. If a subject would like to change their meal preferences, they will be permitted to do so as long as the change can be accommodated by the BWH Nutrition Core. They will be asked to finish meals and log any deviations of the eucaloric diet. For each day with an ad lib diet, caloric intake and macronutrient composition will be calculated and analyzed with Nutrition Data System for Research software after each meal and snack. Subjects will order these meals from a prepared ad lib menu.

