metabolic and stress markers will be collected during each visit. Blood samples will be collected repeatedly up to every 30 minutes during each visit. Blood will be drawn without interrupting sleep using an approximately 72" long IV line from outside the room and a blood-sparing technique to minimize blood loss. If issues with the IV occur, then select samples, up to 2 per wake episode may be drawn via venipuncture. Core Body Temperature will be measured with an oral thermometer. Hunger will be measured under both eucaloric and ad lib dietary conditions by administering Hunger Visual Analog Scales. On the day of admission, reproductive hormone levels will be tested, a urine pregnancy test will be performed, and morphometric measures will be gathered. During the inpatient stay, subjects will complete various questionnaires and tasks (e.g. Food Preference Questions, the Dutch Eating Behavior Scale, the Positive and Negative Affect Scale, hot flash diaries, reward seeking behavior, PSQI, ISI, PHQ-8). After waking, subjects may complete the post-sleep questionnaire and the CCI IPM Exit Questionnaire, which are regularly administered by CCI inpatient unit staff. Subjects may also complete neurobehavioral testing administered automatically by the computers on the CCI inpatient unit. Throughout the inpatient portions of the study urine voids may be scheduled to be collected approximately every 3 hours when the subject is awake. Unscheduled urine voids during the day or overnight may also be collected. For each void, the urine volume will be measured, and aliquots may be saved for later hormonal, metabolite, or electrolyte analysis of analytes that may be affected by sleep fragmentation and/or changes in hormonal status. Urine samples will be collected and stored per standard techniques. Skin conductance may be measured using the Biolog skin conductance monitor. During the 4 days prior to admission, subjects will receive several days of eucaloric meals from the CCI Nutrition Service, and ad lib breakfast will take place at BWH in order to measure food intake. Subjects will be instructed to standardize their sleep patterns during the 4 days at home, and up to a week beforehand, to extend the standardized routine.

- **Undisturbed procedures only:** Bedtime and wake-up time will be fixed to an 8-hour standardized TST.

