Metabolic endpoints are: 1) fasting morning levels of leptin (primary) adipokines, ghrelin (total, acetylated) (secondary), and 2) the circadian leptin profile (exploratory), calculated as area under curve (AUC) to detect whether the overall profile is lower, as seen in sleep restriction studies, and morning fasting AD levels. Behavioral endpoints are: 1) satiety (primary) and hunger (secondary) on a VAS scale, and 2) daily caloric intake during ad lib meals (exploratory). Analyses of each endpoint will be conducted in parallel as we seek to detect coherence among endpoints and focus on consistency across different outcomes in each hormonal and HF context.

For studies involving treatment or diagnosis, provide information about standard of care at Partners (e.g., BWH, MGH) and indicate how the study procedures differ from standard care. Provide information on available alternative treatments, procedures, or methods of diagnosis.

This study involves the administration of leuprolide to healthy individuals in order to better understand experimentally induced hot flashes. Subjects are healthy individuals who do not have any specific medical diagnosis. The DXA scan is not clinically indicated for women participating in the protocol. Alternative imaging studies are therefore not indicated.

Describe how risks to subjects are minimized, for example, by using procedures which are consistent with sound research design and which do not unnecessarily expose subjects to risk or by using procedures already being performed on the subject for diagnostic or treatment purposes.

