This checklist will be completed by the research coordinator and reviewed by the PI to confirm that all data are correctly obtained. In addition, all study personnel will review study data and discuss QA issues related to protocol adherence. Forms available on our IRB website will be used to keep track of adverse events and minor protocol violations.

Describe explicitly the methods for ensuring the safety of subjects. Provide objective criteria for removing a subject from the study, for example, objective criteria for worsening disease/lack of improvement and/or unacceptable adverse events. The inclusion of objective drop criteria is especially important in studies designed with placebo control groups.

Participants will have a serum pregnancy test at the screening visit to ensure that they are not pregnant, and an additional urine pregnancy test will be conducted immediately prior to leuprolide administration. Subjects will be required to use a barrier method of contraception for the duration of the study and after study completion until menses resume. These procedures will serve to minimize the likelihood that study participants become pregnant during study procedures and during

the period of medication exposure.

Participants will receive safety follow up calls regularly after study completion to ensure that menses resume and that, where applicable, that hot flashes resolve. If menstrual cycles do not return to normal or hot flashes do not resolve within several months of follow-up after the completion of all study procedures, participants be referred to an endocrinologist for further evaluation. We have used the same safety procedures in previous studies.

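### No mood or adverse-event question is scheduled after Sleep Block 2, and the later calls are stated to cover only menses and hot flashes

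*Protocol*

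**What the plan says.** Protocol, Study Procedures Overview, Follow-up Phase: the coordinator phones "4 weeks after the final study visit and every 4 weeks thereafter to confirm resumption of menses and cessation of hot flashes". The referral rule in that phase covers the same two items. Women whose menses have not returned, or "who continue to have hot flashes 4 months after receiving the leuprolide injection (3 months after final visit) will be referred", go to their usual medical provider. The only other data collected in this phase are food and appetite records.

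Protocol, methods for ensuring the safety of subjects: participants get "safety follow up calls regularly after study completion to ensure that menses resume and that, where applicable, that hot flashes resolve". The same part says mood will be assessed repeatedly over the study as standard safety monitoring, and that a psychiatrist is available for women with significant depression.

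Protocol, Detailed Description of Sleep Blocks: the questionnaires completed during the inpatient stay include "the Positive and Negative Affect Scale, hot flash diaries, reward seeking behavior, PSQI, ISI, PHQ-8". These are the last mood measures that any section places at a stated time. The Table of Procedures (layout broken in the text available) ends with the Sleep Block 2 column.

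Protocol, Research Design and Methods, Overview: "Behavioral measures will continue to be assessed at home after the 2nd SB is complete". The sentence before it lists negative mood/affect among the secondary and exploratory measures.

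Protocol, Data and Safety Monitoring: adverse events are monitored at visits and recorded by spontaneous reporting. Between visits a woman may contact the investigator.

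Protocol, Foreseeable Risks and Discomforts: leuprolide can stop menses for 2 to 3 months. Hot flashes, emotional lability and depression symptoms are all listed as common effects related to suppression of ovarian steroids. No duration is given for mood effects.

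The SAP does not address safety follow-up.

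**The concern.** The protocol follows two consequences of ovarian suppression, absent menses and hot flashes, until they resolve. It attributes mood symptoms to the same suppression but sets no check on them once Sleep Block 2 is over. The participants are healthy volunteers with no direct benefit, and the consent section acknowledges that the hormonal effect of the depot cannot be reversed on withdrawal.

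The protocol treats severe depression and suicidal or homicidal ideation as grounds for withdrawal and prompt evaluation. An episode that starts after discharge would be found only if the woman contacts the investigator, or raises it on a call made for another stated purpose. The referral route exists. What is missing is a stated question that would trigger it.

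**Working it through.** **Inputs**
- Sleep Block 2 timing: 4 weeks after injection (Study Procedures Overview), or in-lab after at least 4 weeks on leuprolide (Overview).
- Block length: each block "each of which lasts 9 nights/10 days and includes 5 nights of inpatient laboratory assessment" (Detailed Description of Sleep Blocks).
- Calls: 28 days after the final visit, then every 28 days (Follow-up Phase).
- Amenorrhea: 2 to 3 months, taken as 60 and 90 days (Foreseeable Risks).
- Assumption, not in the documents: mood risk lasts as long as amenorrhea.

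**The protocol's own timing figure.** The referral rule equates 4 months after injection with 3 months after the final visit. That puts the final visit at 4 − 3 = 1 month, about day 30, and the first call at 30 + 28 = day 58. Neither reading of the block gives a day-30 end. Adding 3 months (91 days) to a final visit on day 38 gives day 129, and to one on day 33 gives day 124, against 4 months = day 122. The equation is a rounding, good to about a week, so day 58 is not used below.

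**End of Sleep Block 2**
- Whole block starts at week 4: 28 + 10 = day 38.
- Only the in-lab stay must wait until week 4: 28 + 5 = day 33.

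| Quantity | Block ends day 33 | Block ends day 38 |
|---|---|---|
| First call (end + 28) | 61 | 66 |
| Second call (end + 56) | 89 | 94 |
| Unchecked days, 60-day effect | 60 − 33 = 27 | 60 − 38 = 22 |
| Unchecked days, 90-day effect | 90 − 33 = 57 | 90 − 38 = 52 |
| Longest stretch with mood content on calls, 60-day effect | 27 (first call is after day 60) | 22 (same reason) |
| Longest stretch with mood content on calls, 90-day effect | max(61 − 33, 89 − 61, 90 − 89) = 28 | max(66 − 38, 90 − 66) = 28 |

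**Sensitivity**
- A later block start shortens the gap. For illustration, an assumed start on day 42 ends the block on day 52 and leaves 60 − 52 = 8 or 90 − 52 = 38 days.
- Some at-home recording runs for up to 7 days after the block. If it included mood, which no section says, the gaps would fall by 7 days, to 15–20 and 45–50 days.

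**Does any general statement fill the gap?**
- Mood assessment over the whole study: no instrument or time is attached, and the safety text places the calls after the study is complete.
- Behavioral measures continuing at home: the preceding sentence mentions negative mood/affect, so the wording is open. However, Study Endpoints defines the behavioral endpoints as satiety, hunger and caloric intake, and the Follow-up Phase names only food and appetite measures.
- Adverse events at every visit: the Follow-up Phase lists calls, not visits.

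**The case against.** The strongest reply is that mood monitoring is already promised. The commitment to repeated mood assessment sits in a paragraph on leuprolide-specific harms. The Follow-up Phase is listed as one of the study's own phases, and the calls are labelled safety calls. The protocol also promises evaluation and referral, including emergency evaluation, for severe depression during the study, and describes close contact with staff. Haemoglobin is rechecked at study completion, a contact whose timing is not given. The document is a protocol summary that asks for brief descriptions, no call script is included, and a stated purpose is not a full script. The protocol adds "We have used the same safety procedures in previous studies".

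Much of this stands. The intent is ambiguous, and a coordinator may well ask about mood. A reader might infer that women are left without psychiatric cover after discharge, or that nobody will ask how they feel. The documents do not support that: the calls exist, women can contact the investigator, and a psychiatrist is available. The finding is only that no mood or adverse-event question is scheduled for this period. If the investigators already intend one, the amendment simply records it.

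The yield is also likely to be low. The protocol puts clinically significant depression at 2–3% in closely monitored volunteers. For 40 completers that is 0.02 × 40 = 0.8 to 0.03 × 40 = 1.2 cases over the whole exposure, not just the gap. Current depression, past major depressive or bipolar disorder, current ideation and prior suicide attempts are excluded. Late cases may be undercounted in that rate, but the documents do not show whether they are.

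Finally, adding content to existing calls does not help if the effect lasts only 60 days. That is correct.

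**Conclusion.** The point holds as a low-cost safety improvement. On the text, the calls after Sleep Block 2 are for menses and hot flashes, and nothing schedules a mood or adverse-event question after that block.

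The size of the gap is 22–27 days for a 60-day effect and 52–57 days for a 90-day effect. This rests on a block ending about day 33–38 and on the assumption that mood risk lasts as long as amenorrhea. It would be tempting to read the 2 to 3 months of amenorrhea as the protocol's own duration for mood risk, but the protocol gives none. The gap concerns scheduled, active questioning only, since participant-initiated contact remains open throughout. The number of cases arising in it is unknown and probably small.

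**What to change.** In the Follow-up Phase text, add three items to each existing call: the PHQ-8, a direct question on suicidal or homicidal ideation, and an open adverse-event question. The ideation question is needed because the PHQ-8 does not ask about it; the eligibility criteria already list the two separately. Apply this to every woman who received leuprolide, including those who withdraw, and refer positive answers to the psychiatrist already described in the safety text. State there that the mood-monitoring commitment extends to these calls.

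The cost is a short amendment, a few minutes per call, an escalation instruction for the coordinator, and a clinician who can be reached on call days. In the 90-day case the longest unchecked stretch falls from 52–57 to 28 days. In the 60-day case nothing changes.

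Optionally, one extra call 2 weeks after discharge would shorten the 60-day case. With a day-38 end the call falls on day 52 and the longest stretch is max(14, 60 − 52 = 8) = 14 days. With a day-33 end it falls on day 47 and the longest stretch is max(14, 60 − 47 = 13) = 14 days. It adds one contact per woman, and the main change does not depend on it.

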- **Procedures to occur in both SB_{UD} and SB_{SF}:** Subjects will remain indoors during each admission. Technicians will hook subjects up to a PSG monitor each night. Participants will be given a standardized eucaloric diet for the first 5 days of their visit, and will have an ad lib menu on the 6th day of their in-lab stay. On the 6th day, subjects will be given food provided by the Nutrition Core for that entire day, and will be allowed to consume as much as desired at home while logging their meals, snacks and drinks with the app MealLogger™. Subjects will be expected to finish these meals. Caloric and macronutrient intake will be quantified. Fasting adipokine levels, other

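### The sixth-day ad lib text also tells subjects to finish their food, which compromises that day as a measure of free intake

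*Protocol*

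**What the plan says.** - **Protocol, Detailed Description of Sleep Blocks, procedures common to the undisturbed and fragmented conditions.** "Participants will be given a standardized eucaloric diet for the first 5 days of their visit, and will have an ad lib menu" on the sixth day. On that day subjects receive Nutrition Core food and "will be allowed to consume as much as desired at home while logging their meals, snacks and drinks with the app MealLogger". The next sentence reads "Subjects will be expected to finish these meals". The one after it says that calories and macronutrients will be quantified.
- **Same section, at-home procedures.** Days 1, 2 and 4 are eucaloric. Day 3 is ad lib: "On the 3rd day, subjects will be given food provided by the Nutrition Core for that entire day", with free intake and meal logging. The only finish instruction here is "They will be asked to finish meals and log any deviations of the eucaloric diet". For ad lib days, "Subjects will order these meals from a prepared ad lib menu".
- **Protocol, Overview.** The eucaloric diet runs before admission "as well as for the first four days of the inpatient visit". Ad lib eating falls on one day before admission and on the last inpatient day.
- **Protocol, Study Endpoints, and SAP, Analysis approach.** Ad lib caloric intake is exploratory. Fasting leptin and satiety are the primary metabolic and behavioral endpoints. Hypothesis 1b predicts that fragmentation raises hunger and caloric intake.

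**The concern.** A free-intake measure is informative only if the subject stops eating when she wants to. An instruction to finish the food replaces part of that decision with the amount on the tray. Here the instruction stands between the sentence granting free intake and the sentence announcing its measurement, and the nearest meals it can refer to are the ad lib ones. Staff working from that paragraph would give it on the measurement day.

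The other ad lib day has no such instruction. The two days that bracket the fragmented nights may therefore differ in what subjects were told as well as in how they slept, and the analysis cannot separate the two. Caloric intake is exploratory, but Hypothesis 1b names it, and the SAP intends to look for coherence across endpoints. A distorted intake result would therefore affect the overall reading.

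**Working it through.** **1. What the finish sentence refers to.** Read in order, it refers to the sixth-day ad lib food. It could be a displaced eucaloric instruction, since the paragraph opens with the eucaloric diet and the at-home bullet ties finishing to that diet. On either reading the text is wrong where it stands.

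**2. Where the ad lib days fall.** The detailed description gives each block 5 in-lab nights, 2 undisturbed and 3 fragmented. The Overview gives 10 nights in total, and the compensation schedule agrees: 100 + 55 + 250 + (10 × 275) + (2 × 700) + 3,500 = 8,055 dollars, the stated maximum. With one five-night admission per block, the third at-home day precedes every fragmented night and the sixth in-lab day follows all three, whatever their order. The instruction then falls on one side of the before/after comparison.

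**3. Which contrasts are exposed.** Under the SAP, Hypothesis 1b compares fragmented with undisturbed sleep within each block. Hypothesis 1c compares undisturbed with undisturbed, Aim 2 compares like sleep states before and after leuprolide, and Aim 3 compares hormonal states within each sleep state. For the last three, a day-specific instruction is on both sides or on neither.

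**4. Direction and possible size.** The plan has no figure to reproduce. Its sample-size calculation concerns leptin correlations, and no mean, SD or served amount is given for intake. Assumptions, for illustration only: free intake has mean μ = 2,000 kcal, between-subject SD 350 and within-subject SD 250, so σ = √(350² + 250²) ≈ 430. Let S be the amount served.

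- Intake strictly fixed on day 6 only: shift = S − μ.
- Floor on day 6 only (finish the serving, more allowed): shift = (S − μ)Φ(d) + σφ(d), with d = (S − μ)/σ. For S = 2,300: 300 × 0.757 + 430 × 0.313 ≈ 362.
- Floor on both days: the null contrast is 0. The last column shows what remains of an assumed true effect of +150 kcal.

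| S (kcal) | Fixed, day 6 only, no true effect | Floor, day 6 only, no true effect | Floor on both days, true +150 |
|---|---|---|---|
| 1,700 | −300 | +62 | 121 |
| 2,000 | 0 | +172 | 85 |
| 2,300 | +300 | +362 | 45 |
| 2,600 | +600 | +616 | 17 |

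If subjects order for themselves and finish everything, over-ordering by 5% to 20% on day 6 only adds 0.05 × 2,000 = 100 to 0.20 × 2,000 = 400 kcal. No over-ordering adds nothing. Proportional over-ordering on both days creates no spurious difference and slightly stretches a true one (at 10%, 150 × 1.10 = 165).

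**5. Diet-day count.** Five nights span six calendar days. The detailed description fills them: 5 eucaloric + 1 ad lib = 6. The Overview gives 4 + 1 = 5 and leaves one day unassigned. The detailed description also counts the sixth day as part of the in-lab stay yet has the food eaten at home, while the Overview places ad lib eating on the last inpatient day.

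**The case against.** The strongest reply is that this is a misplaced sentence. Finishing belongs to the eucaloric diet in the at-home bullet, and the Overview treats ad lib intake as an outcome, which a finish rule would defeat. That may well be the intent. It does not remove the need to correct the text that staff follow.

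A reader might infer that intake is fixed at the amount served. The documents do not support that: subjects choose from a menu and may eat freely, and portion sizes and refills are not stated. Finishing sets at most a floor.

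A reader might also infer that the bias favors the hypothesis. That is not established. If both sentences are honored and the instruction applies on the sixth day only, none of the illustrative shifts is negative, so upward is the most plausible direction. A common floor on both days would instead shrink a true effect. The layout of admissions is itself unclear: the procedures overview describes two five-night stays per block, the paragraph in question covers both sleep conditions, the SAP mentions randomization order, and the schema is not shown. If each condition had its own stay, the instruction would sit on both sides of the contrast.

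**Conclusion.** The point stands as a conflict in the protocol text with a possible effect on one exploratory endpoint. As written, a finish instruction applies on a day meant to measure free intake, and the matching ad lib day lacks it. The contrast for caloric intake under Hypothesis 1b can be distorted, most plausibly upward if the instruction applies on the sixth day only and toward the null under a common floor on both days. The size cannot be stated; the kilocalorie figures above rest wholly on assumed intakes and servings.

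Two wider inferences are not supported. Spurious inflation does not carry to Hypotheses 1c, 2 and 3, which compare like sleep states. Nor is harm to the primary fasting leptin endpoint shown: the day of the last fasting sample is not given, and a fasting sample on the last morning would precede that day's ad lib eating. The four-versus-five-day discrepancy leaves the diet on the preceding day unclear and should be resolved, but it does not demonstrate an effect on leptin.

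**What to change.** 1. In the procedures common to both sleep conditions, attach the finish instruction to the eucaloric meals only, matching the at-home text.
2. State that neither ad lib day carries a finish instruction, and that both use the same instruction, setting and logging. At present the third-day ad lib breakfast is taken at the hospital, while the sixth-day food is described as eaten at home.
3. Reconcile the Overview with the detailed description on four versus five inpatient eucaloric days, and on whether the final ad lib day is spent in the lab or at home.
4. Establish what subjects were actually told. If only some received the finish instruction on an ad lib day, flag those days in a sensitivity analysis of caloric intake. If all did, excluding them would leave little to contrast, so report it as a limitation of that endpoint.

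The cost is a few sentences in the protocol and staff instructions and, at most, one sensitivity analysis. No sample-size or primary-analysis change is needed.
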